## **5. LIMITATIONS**

- The real-life observational studies are only complimentary to the clinical trials

## **6. STUDY CONDUCT, MANAGEMENT & ETHICS**

### **6.1. Ethical Approval and Subject Consent**

This study will comply with all applicable laws regarding subject privacy. No direct subject contact or primary collection of individual human subject data will occur. Study results will be in tabular form and aggregate analyses that omits subject identification. The Polish ethics committee approval is required. Any publications and reports will not include subject identifiers.

### **6.2. Adverse Event (AE), Pregnancy Exposure, and Incident Reporting**

The planned study is a retrospective analysis. All the adverse events (AEs) and serious adverse events (SAEs) resulting in therapy termination will be scrutinized and qualitatively analysed.

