## **2. OBJECTIVES**

To evaluate the efficacy of mepolizumab 100 mg SC every 4 weeks in patients with severe eosinophilic asthma who have been treated for at least 12 months in several Polish allergy/asthma centres under the same protocol .

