## **3. RESEARCH METHODOLOGY**

### **3.1. Study Design**

Retrospective multicentre observational study will involve 130 patients with severe eosinophilic asthma ( SEA ) who have been treated in six Severe Asthma Treatment Centres ( SATCs) in Poland.

In each SATC all data available in the program questionnaires will be transferred to the Study Data Sheet (questionnaire), and will be send to the study coordinator within 5 months from the study beginning

The start-up meeting including partners from all centres involved will be organized to discuss the study protocol and to unify data collection

The evaluation parameters (exacerbations rate, OCS dose) will be analysed at least at three time points: pre-MEPO, after 24 weeks of MEPO and after 1 year of MEPO administration (some of the outcomes will be observed every 4 weeks, for the details see 'study endpoints' section).

In addition the following parameters which are available in patients' records will be analysed:

- ACQ-5 score (measured at qualification for the treatment and every 4 weeks thereafter)
- AQLQ score (measured at qualification for the treatment and every 4 weeks thereafter)
- Pre-bronchodilator FEV1 (measured at qualification for the treatment and every 4 weeks thereafter)

Research activities will include:

- collecting raw data from the clinical centres (paper version) and constructing a raw dataset (digital version),
- data cleaning, computation of variables,
- statistical analysis typical for pre-post study design (the statistical analysis will be outsourced to the specialized private institute).

Clinical improvements observed at 24 weeks and at 52 weeks of treatment with Mepolizumab will be referred to the following characteristics of patients at baseline:

- demographics,
- presence of comorbidities including the atopic status,
- concomitant pharmacotherapy,
- clinical status,
- eosinophilia.

We will control for mepolizumab use regarding dose, treatment duration and dosing frequency as well as for the safety profile based on the AEs reporting in the medical documentation.

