### **3.2. Data Source / Data Collection**

Patients recruited to the study had been treated with mepolizumab between December 2017 and December 2019.

All the data planned to be used in the proposed study were systematically collected in the form of the clinical documentation (paper version) and will be transferred in the study centres into the study Data Sheets.

Collaborating Researchers (Severe Asthma Centres' Leaders) will provide the data input into the dedicated online questionnaire.

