### **3.3. Study Population**

130 Patients who were treated with mepolizumab in six severe-asthma clinics in Poland between December 2017 and December 2019. In the drug program in Poland it was mandatory to conduct the control examinations at the 24th and 52nd week of the treatment. In the proposed study we will use this information to evaluate study endpoints. Only patients who have been treated for at least 52 weeks are included into the study

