#### **3.3.1. Inclusion Criteria**

- The availability of the complete data

- Duration of treatment with mepolizumab:  $\geq 52$  weeks
- Satisfying the Polish drug programme inclusion criteria:
  - Age  $>18$
  - Before treatment with mepolizumab (BSAT inclusion criteria):
    - High doses of ICS + one other controlling medication (i.e. LABA)
    - $\geq 2$  exacerbations in the previous year
    - $\geq 350$  eosinophil cells/ $\mu\text{l}$  in the blood at the time of qualifying, or in the previous year
    - Pre-bronchodilator FEV1  $< 80\%$

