## **3.5. Sample Size**

Retrospective multicentre observational study will involve 130 patients with SEA who have been treated in six severe asthma treatment centres in Poland. The sample includes all individuals who participated in the drug programme in Poland at least for 52 weeks between December 2017 and December 2019

The motivation to focus on this sample was the following:

- a relatively large sample of patients (N=130),
- the unique and complete dataset containing patients' characteristics and treatment results (all severe asthma centres participating in the drug programme are obliged to collect all the data we use in this study),
- the opportunity to study the treatment results under the unique inclusion criteria of the Polish drug programme ( $\geq 350$  eos/ul) (see 3.3.1).

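### Section 6.2 plans to review all adverse events that ended therapy, but as the study set is defined no termination before week 52 can appear in it

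*Combined protocol and SAP*

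**What the plan says.** Section 6.2 describes the study as a retrospective analysis and sets one safety task: "All the adverse events (AEs) and serious adverse events (SAEs) resulting in therapy termination will be scrutinized and qualitatively analysed". It does not say in which patients. Section 3.1 adds that the study will control for mepolizumab use "as well as for the safety profile based on the AEs reporting in the medical documentation", again without naming a separate population.

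The study set is defined consistently elsewhere:

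- Section 2 sets the objective in patients "who have been treated for at least 12 months in several Polish allergy/asthma centres".
- Section 3.3: "Only patients who have been treated for at least 52 weeks are included into the study".
- Section 3.3.1 makes 52 weeks or more of mepolizumab an inclusion criterion. Section 3.3.2 makes less than 52 weeks an exclusion criterion.
- Section 3.5: "The sample includes all individuals who participated in the drug programme in Poland at least for 52 weeks between December 2017 and December 2019". The number given is 130, from six centres.

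On data collection, section 3.1 states: "In each SATC all data available in the program questionnaires will be transferred to the Study Data Sheet (questionnaire". Section 5 contains a single general sentence on the place of real-life studies beside clinical trials and does not mention selection on treatment duration.

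**The concern.** The review is meant to cover every adverse event that ended therapy. A patient whose therapy ended for an adverse event in the first year has, by that fact, less than 52 weeks of treatment and is excluded. The review would then be run on a set from which its first-year cases have been removed.

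What is at stake is how the result is read. A report that lists few or no treatment-ending events looks reassuring, and section 7 plans presentation and publication. For the first year, however, that finding would be produced by the eligibility rule. Nothing in section 5 would tell the reader so.

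**Working it through.** **Step 1. Set the sections side by side.**

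| Element | Section | Content |
|---|---|---|
| Event to be reviewed | 6.2 | Adverse event leading to termination of therapy |
| Population for the review | 6.2 | Not stated |
| Study set | 2, 3.3, 3.3.1, 3.5 | At least 52 weeks of treatment |
| Explicit exclusion | 3.3.2 | Less than 52 weeks of treatment |
| Wider safety set, starter log or count of early stoppers | None | Not defined |

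**Step 2. Consequence.** Let T be the time from first dose to permanent termination. The study set requires T ≥ 52 weeks, and a first-year termination is T < 52 weeks. Therefore

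P(T < 52 weeks | T ≥ 52 weeks) = 0,

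whatever the true first-year risk. The count among the 130 is 0 if that risk is 1% and 0 if it is 10%, so it carries no information about the risk. Two things remain observable: terminations at or after week 52, and adverse events in the first year that did not end treatment.

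**Step 3. How many could be missing.** The plan gives no termination rate, no number of starters and no stop reasons, so it offers no figure to reproduce. The 130 in section 3.5 is a count of available patients with no design inputs. For illustration only, let p be the share of starters who stopped for an adverse event in year one, and suppose first that nobody stopped early for another reason. Starters are patients who either stopped before week 52 or reached it; late starters still on treatment are left out. Then

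starters = 130/(1 − p), and missing terminations = 130p/(1 − p).

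| Assumed p | Starters | Missing terminations |
|---|---|---|
| 1% | 130/0.99 = 131.3 | 1.3 |
| 2% | 130/0.98 = 132.7 | 2.7 |
| 5% | 130/0.95 = 136.8 | 6.8 |
| 10% | 130/0.90 = 144.4 | 14.4 |

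Rounding starters up to whole patients gives 2, 3, 7 and 15.

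**Step 4. Direction of the error.** If a further share q of starters stopped early for other reasons, the formula becomes 130p/(1 − p − q), which is larger for any q > 0. Likewise, if the complete-data criterion removed some patients who did reach week 52, the starters behind the 130 are more numerous. The table therefore gives lower bounds for each assumed p.

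**The case against.** The strongest reply is that the absence of a wider set is inferred from silence. Section 6.2 says all, names no population, and may have been meant to include patients who stopped. Section 3.1 transfers all available programme data and does not limit that sentence to the 130. This is fair as a caution about intent, but it does not rescue the text. Section 3.3.2 explicitly excludes shorter treatment, and no section brings those patients back for safety. If the wider review was intended, the protocol has to say so.

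A second reply is that the weight is small. The only objective is efficacy, safety is not among the listed endpoints, the review is qualitative, and the 52-week rule is openly stated in several sections. This stands and limits the consequence to the safety item. It does not remove the mismatch, because section 5 never tells the reader what the rule does to a review of terminations.

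A reader might also infer more than the documents support:

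- *That section 6.2 is empty, because observation ends at week 52.* Sections 3.1 and 3.4 schedule ACQ-5, AQLQ and FEV1 every four weeks with no stated end. Section 3.1 takes adverse events from the medical documentation, which the week 24 and 52 schedule for exacerbations and oral corticosteroid dose does not bound.
- *That December 2019 closes adverse event observation and so caps follow-up after week 52.* Section 3.2 says "Patients recruited to the study had been treated with mepolizumab between December 2017 and December 2019". That dates treatment; no section sets a cut-off for adverse event records.
- *That the plan would publish zero out of 130 as a first-year risk.* Section 6.2 plans no rate and no denominator. The danger is a misreading by others, not a planned estimate.

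**Conclusion.** The point holds in this form: read with the eligibility rules, section 6.2 cannot capture any termination before week 52, and section 5 does not warn of it. This is a stated analysis that cannot deliver its stated content for the first year of treatment. It should be fixed, but it is confined to the qualitative safety item and leaves the efficacy endpoints untouched.

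The core conclusion needs no outside figure. It rests on termination meaning a permanent stop, and on the eligibility rules applying to the review, which is the likelier reading since no other population is named. The size is unknown: at least about 1 to 14 missing terminations holds only under assumed first-year stopping of 1% to 10% for adverse events, a range the documents neither support nor contradict.

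**What to change.** **Preferred.** In section 6.2, apply the termination review to all patients at the six centres who received at least one dose of mepolizumab in December 2017 to December 2019, without the 52-week and complete-data criteria. Report:

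1. the number of starters;
2. the number who stopped before week 52, with the recorded reasons;
3. separately, the number still on treatment with less than 52 weeks, so that late starters are not taken for stoppers.

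Keep the review qualitative and the efficacy set as it is.

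*Cost:* protocol wording and a limited extra extraction (start date, stop date, recorded stop reason) beside the five-month collection in section 3.1. The ethics approval required by section 6.1 must cover the added records. The number of added patients is not known from the documents. Section 3.5 says centres must collect the programme data, but nothing confirms that stop reasons were recorded, so some may be missing.

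**If the records do not allow this.** Restrict the section 6.2 sentence to terminations at or after week 52, and state in section 5 that selection on 52-week persistence prevents any conclusion about first-year terminations for adverse events. *Cost:* two wording changes and no extraction. This removes the contradiction but leaves the first year unexamined.

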## **3.4. Variables**

The main outcome variables are listed as the primary or secondary endpoints. Asthma exacerbation is defined as in the Polish drug programme (see 3.4.1.1.).

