## **4. DATA ANALYSIS CONSIDERATIONS**

- Exacerbations rates in 24th and 52nd week with comparison to rate of exacerbations during the pre-treatment year. Also the frequency of exacerbations in 6- and 12-month follow-up period will be described as patient count and percentage as categorical variable (0,1,2,3,4+ exacerbations).
- OCS median doses in 24th and 52nd week with comparison to the median dose at baseline
- ACQ-5, AQLQ, FEV1 measured on the monthly basis, the mean score at baseline will be compared with every post-treatment monthly score.
- Blood eosinophil geometric mean in 24th and 52nd week with comparison to the geometric mean at baseline

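### Section 6.2 analyses adverse events that ended therapy, but the cohort is restricted to patients treated for at least 52 weeks, so essentially no first-year AE or SAE has a specified analysis

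*Combined protocol and SAP*

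**What the plan says.** Four parts of the combined protocol and SAP bear on this point.

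- **Section 3.1 (Study Design)** says the analysis will control for how mepolizumab was used, "as well as for the safety profile based on the AEs reporting in the medical documentation". It does not limit this to events that ended treatment.
- **Section 6.2** gives the only rule for analysing adverse events: "All the adverse events (AEs) and serious adverse events (SAEs) resulting in therapy termination will be scrutinized and qualitatively analysed".
- **Section 3.3** fixes the population: "Only patients who have been treated for at least 52 weeks are included into the study". Sections 3.3.1 and 3.3.2 repeat the 52-week limit as an inclusion and an exclusion criterion.
- **Sections 3.4 and 4** list variables and analyses for exacerbations, OCS dose, ACQ-5, AQLQ, FEV1 and blood eosinophils. Neither contains an AE variable or an AE summary.

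The objective in section 2 concerns efficacy alone: "To evaluate the efficacy of mepolizumab 100 mg SC every 4 weeks in patients with severe eosinophilic asthma".

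**The concern.** Section 3.1 brings safety into the study, but the rule meant to deliver it selects events by a criterion that the eligibility rule almost excludes. A patient who had a serious event in month four and went on to complete the year is in the cohort and may have the event in the record. It did not end therapy, so the 6.2 rule does not reach it and no other section says what will be done with it. A patient whose event did end therapy in month four is not in the cohort.

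The stakes lie in how the report will read. Followed as written, it could contain very few safety events for reasons of design, and section 7 plans conference presentation and publication. Section 5 has no caveat on safety, so a reader could not tell an absence of harm from an absence of analysis.

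**Working it through.** The plan states no figure on this point, so the main check is a comparison of the sections.

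**Step 1. What each section covers.**

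| Section | Population or events covered |
|---|---|
| 3.1 | Safety profile from AE reporting in the records; no restriction by consequence |
| 6.2 | AEs and SAEs that ended therapy; qualitative analysis |
| 3.4 | No AE variable |
| 4 | No AE or SAE summary |
| 3.3, 3.3.1, 3.3.2 | Only patients with at least 52 weeks of treatment |

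**Step 2. Combine 6.2 with 3.3.** Let T be the time at which therapy ended.

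- Inclusion requires T to be at least 52 weeks, or therapy to be still running.
- The 6.2 rule selects an event only if it caused therapy to end at T.
- Within the cohort, the rule can therefore select only events with T at or after week 52.

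An event that began in the first year can qualify only if it began before week 52 and led to stopping at or after week 52. Hence the qualifier: essentially no first-year event, rather than strictly none.

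**Step 3. How much time the 6.2 rule has to work in.** Section 3.2 places treatment between December 2017 and December 2019, about 24 months. The first 12 are protected by eligibility. The time left per patient is at most about 24 − 12 = 12 months, for someone who started at the beginning. It is about zero for someone who started in December 2018. The efficacy analyses in section 4 compare baseline with assessments up to week 52. The rule for safety events and the window for efficacy thus barely overlap.

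**Step 4. Does another section fill the gap?** Section 3.1 also mentions dose and dosing frequency, so a delayed dose may appear as exposure information, but nothing links it to an AE. Exacerbations are counted in section 4, but as an efficacy outcome. No section supplies an AE analysis for patients who continued.

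**Step 5. Illustration of scale.** The documents give no AE or SAE rate, so these one-year risks p of a non-terminating SAE are assumptions, the same for each patient and independent between patients. Section 3.5 gives the number: "Retrospective multicentre observational study will involve 130 patients with SEA". The expected number affected is 130p, and the chance that at least one is affected is 1 − (1 − p)^130.

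| Assumed p | Expected patients, 130p | Chance of at least one |
|---|---|---|
| 1% | 1.3 | 73% |
| 2% | 2.6 | 93% |
| 5% | 6.5 | 99.9% |

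This shows only that some such patient is likely across the range. It does not measure bias in any planned result, and Steps 1 to 4 do not depend on it.

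**The case against.** The strongest case on the other side has five parts.

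- **Safety is not an objective.** Section 2 is about efficacy, and section 3.4 says of its outcomes that "The main outcome variables are listed as the primary or secondary endpoints"; none concerns safety. How much AE detail to abstract in an efficacy-focused chart review is partly a design choice. This stands as a reason for moderate severity. It does not remove the mismatch, because 3.1 introduces safety and 6.2 sets a rule for it.
- **Section 6.2 does not say that other events will be discarded.** A reader might infer that non-terminating events will never be analysed, or that 3.1 promises an analysis of every AE. The documents support neither. Section 6.2 does not confine itself to the events it names, it sits under study conduct and ethics, and 3.1 is a loose statement of intent that implies some use of AE records. What the text supports is that no analysis is specified for these events.
- **The wording is ambiguous.** The restriction to terminating events could grammatically attach to SAEs alone. That would mean analysing all AEs but only some SAEs, which is implausible, and non-terminating SAEs would still lie outside the SAE rule. The sentence needs clarifying on either reading.
- **Section 6.2 may be meant for patients outside the cohort who stopped early.** That would make sense of it, but no section defines such a group or says that its data will be collected. First-year events in the included patients would remain without an analysis.
- **Feasibility is unknown.** The Study Data Sheet is not in the documents, so it may already hold AE fields, or the source records may lack onset and seriousness. This stands, and the fix is worded accordingly.

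A reader might also infer that the study intends to claim good tolerability. No section plans such a conclusion; the risk lies in how a sparse safety section might be read.

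**Conclusion.** The point holds in this form: sections 3.1 and 6.2 differ in scope, sections 3.4 and 4 do not close the gap, and the 52-week rule in 3.3 leaves 6.2 with essentially nothing to select from the first year. The safety profile mentioned in 3.1 cannot be obtained from the rule in 6.2.

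This rests on taking the termination condition in 6.2 to apply to both AEs and SAEs, and on counting as terminated only treatment that ended for good. The number of events concerned is unknown. The 1.3 to 6.5 patients shown above follow from assumed risks of 1% to 5% that the documents neither support nor contradict.

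The plan should be changed, but the matter is not critical: no efficacy endpoint is affected. Widening the event rule alone would not be enough, because AE percentages among patients who completed a year are selected towards good tolerance.

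**What to change.** 1. **Section 6.2:** extend the analysis to all AEs and SAEs recorded in the medical documentation from the first mepolizumab dose to the end of available follow-up, whether or not treatment ended, with the first 52 weeks reported separately. Keep the qualitative narrative for serious and terminating events.
2. **Data Sheet:** record seriousness and the action taken on mepolizumab for each event, where the records give them.
3. **Section 4:** report the number and percentage of patients with at least one AE and with at least one SAE.
4. **Early stoppers:** where centre records allow, report how many patients started mepolizumab but stopped before week 52, and how many of these stopped because of an AE.
5. **Section 5:** state that the AE figures come from patients who completed one year and from routine records, and so are likely to understate harm.

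The cost is somewhat longer abstraction from records that are already being transcribed, a revised paragraph and one table. How much longer depends on what the Data Sheet already holds. Counting early stoppers needs a further request to the six centres.

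If the sponsor prefers the narrow scope, the alternative is to withdraw the safety-profile statement in 3.1 and state that the study cannot support a conclusion on tolerability.

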## **7. PLANS FOR DISSEMINATING AND COMMUNICATING STUDY RESULTS**

The study results are planned for external distribution (presentation at conferences and publication). The study will be closed upon sign-off of the final report document. Manuscript development activities will follow the final report sign-off. Planned Publication date (manuscript): October 2020.

